
We have been approved for funding by Department of Defense (DoD) to support for a 4-year multicenter RCT of TH+NMB for 48h vs. standard of care with contract to be completed June 1, 2020 and with enrollment to begin in Fall of 2020. This study was designed prior to the onset of COVID-19, which is now the most common cause of ARDS and will likely continue to be in the Fall, 2020 and perhaps beyond. Therefore, it is important to decide whether patients with COVID-19 ARDS should be enrolled in our CHILL trial. Therefore, we will conduct a 20-patient pilot safety and feasibility trial of our CHILL TH+NMB treatment vs. control in COVID-19 patients with ARDS who meet the inclusion/exclusion criteria of our DoD-funded trial. The major objective of the proposed pilot trial is to determine whether it is safe and feasible to include patients with COVID-19 ARDS in our Phase IIb CHILL RCT of TH+NMB vs. control in patients with moderate to severe ARDS.

The pilot will be conducted at the University of Maryland Medical Center. To facilitate randomization within the inclusion window, we will consent and enroll based on partial fulfillment of randomization criteria and randomize once all criteria are met. Patients will be

eligible for enrollment when they have been diagnosed with COVID-19 by PCR, and have met all Berlin criteria for moderate to severe ARDS within the 48h inclusion window except the P/F ratio  $\leq 200$  but will not be randomized until P/F ratio (measured or imputed based on SpO2) is  $\leq 200$  (while on  $\geq 8$  cm H2O PEEP and  $\geq 0.6$  FiO2). We plan to randomize a total 20 patients over 4 months to hypothermia (core temperature 34°-35°C for 48h) plus NMB or usual temperature management. The primary outcome measures will be effectiveness of cooling in achieving and maintaining the target temperature and safety measures. Secondary outcomes will include 28-day ventilator-free days (VFDs), 28-day ICU-free days, oxygen saturation index (OSI), driving pressure, Sequential Organ Failure Assessment (SOFA) score, 60-day and 90-day survival, 90-day functional assessment, cognitive assessment at ICU and hospital discharge, and biomarkers of inflammation and lung injury. Since the nature of the intervention precludes blinding, all treatment and clinical decision making related to study outcomes will be protocolized and compliance with study protocols will be monitored.

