### 1.2/ Study Aims and Objectives

We will conduct the CHILL-pilot single-center RCT of TH in patients with COVID-19 and ARDS with P/F < 250 to address the following specific aims:

1. **Aim 1: Analyze the safety and feasibility and the potential lung protective effect of treating patients with COVID-19 infection and ARDS with P/F < 200 with mild TH (core temperature 34°-35°C) + NMB for 48h compared with controls receiving standard temperature management.** We expect the TH-treated group to achieve targeted temperature within 4h of randomization and to maintain TH for 48h without significant increase in serious adverse effects compared with the control arm.
2. **Analyze the potential lung protective effect of mild TH (core temperature 34°-35°C for 48h) and NMB in patients with ARDS and P/F < 200 compared with controls receiving standard temperature management.** We expect the TH-treated group to trend toward having more 28-day VFDs (primary) and 28-day ICU-FDs, and improved day-3 driving pressure and OSI than the controls.
3. **Evaluate the effects of TH on systemic inflammation and extrapulmonary organ dysfunction.** We expect the treated group to have reduced levels of proinflammatory mediators and lower Sequential Organ Failure (SOFA) scores than controls.

The proposed pilot study will determine whether we can safely include patients with COVID-19 and ARDS in our larger Phase IIb trial of TH and NMB in patients with ARDS. It will help us determine whether the 48h duration of cooling is sufficient.

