##### 2.2.1.1.1 Responsibilities of the CEC:

1. The CEC will meet bi-weekly to monitor progress with enrollment, randomization, retention, and data quality milestones and re-evaluate and revise as needed all study protocols.
2. The CEC will review suggestions for protocol amendments from all CHILL-pilot personnel and make final decisions about modifying protocols.
3. [name] will prepare reports for DSM meetings with input from [name].
4. Serious/Reportable Adverse Event (SAE/RAE) Adjudication and Reporting: The following is an initial plan for adverse event (AE) reporting (the plan will be revised by the CHILL leadership with input from CHILL personnel and the CHILL Data Safety monitor, [name], based on experience with the ongoing study). Serious Adverse Events are defined as any deaths, life-threatening events, or events that prolong hospitalization that occur within the first three study days (which includes the period of cooling and rewarming in the Therapeutic Hypothermia arm). All SAEs will be reviewed by [name] based on information provided by [name]. [name] will report the SAE, including his assessment of relatedness to study procedures, to the UMB IRB and the Data and Safety Monitor, [name] within 48 hours of discovery. Reportable AEs (RAEs) that do not meet the threshold for SAEs are defined as any clinically important untoward medical occurrence in the first study week which is different from what is expected in the clinical course of a patient with ARDS. All other AEs will be tabulated without case-by-case review unless a difference between treatment groups calls for review of a group of cases. [name] will submit monthly tabular reports of all SAEs/RAEs to [name] and will submit tabular summaries of all AEs to [name] every 6 months. The AE summary will be included in the bi-annual review by [name].
5. Ongoing Scientific Review: CEC members and any other interested CHILL-pilot personnel may bring new information with potential impact on study protocols and analysis to the attention of the entire CEC. The topic will be added to the CEC meeting agenda and background information distributed with enough lead time to allow a productive discussion.
6. Processing Requests for Sample Sharing: [name] will provide to the CEC all information about sample sharing requests and information about sample availability

and status of the CHILL-pilot biomarker analysis to inform decisions by the CEC about the priority of sample sharing requests.

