### 2.2.3.2 DSM procedures

The Data Analysis and Management Core (DC) will be responsible for managing Data Safety Monitoring, including preparing reports for bi-annual review by [name]. The following is an initial plan for adverse event (AE) reporting, which will be modified and finalized based on discussions with the DSMB:

1. Clinical site staff will be responsible for recording all AEs on the appropriate CRF.
2. Any deaths, life-threatening events, or events that occur within the first three study days, including NMB, cooling and rewarming, and unexpected SAEs occurring in the first study week will be reviewed by [name] based on information provided by [name].
3. [name] will report the SAE, including his assessment of relatedness to study procedures, to the University of Maryland Baltimore IRB and [name] within 48 hours of discovery.
4. All other AEs will be tabulated without case-by-case review unless a difference between treatment groups calls for review of a group of cases.
5. [name] will submit monthly tabular reports of all SAEs and other RAEs to [name] and will submit tabular summaries of all AEs to [name] every 6 months.
6. Since this is a small pilot study, there are no plans for an interim analysis and early termination based on futility or proven benefit.

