### 3. *Serious*

This will be reported as yes or no.

An AE will be classified as serious if it is fatal or immediately life-threatening (as the reaction occurred, not if it had occurred in a more serious form), permanently disabling, severely incapacitating, or requires or prolongs inpatient hospitalization. Events that may jeopardize the patient and require medical or surgical intervention to prevent one of the previously listed outcomes may also be classified as serious.

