Pilot Randomized Clinical Trial of Therapeutic Hypothermia Plus Neuromuscular Blockade vs. Standard of Care in Patients With Moderate to Severe ARDS - the Cooling to Help Injured Lungs (CHILL) Pilot Study

NCT03376854

Statistical Analysis Plan

Date: May 19, 2020

Statistical Analysis Plan: This is a pilot study of feasibility to demonstrate feasibility and safety to treat patients with COVID-19 and ARDS with our CHILL treatment protocol (hypothermia to core temperature 34-35°C + NMB for 48h) and to determine whether there are any trends toward benefit in the treated group. The primary outcome will be analyzed using descriptive statistics, the mean \pm SD and the median \pm IQR of time to reach the target temperature and the percent of total treatment time within the targeted temperature range. Differences in SAEs will be analyzed by Chi square. The group difference on 28-day VFDs will be tested with a permutation test for the difference in group means with alpha = .05 (two-tailed). This test was chosen due to the large number of zero values expected (based on our open-label pilot and retrospective studies). If the difference on a baseline prognostic variable is statistically significant, we will perform a secondary analysis to adjust for this variable using a regression approach. For secondary clinical outcomes t-tests, Wilcoxon, or chi-square tests will be used as appropriate. Mixed model repeated measures ANOVA will be used to test for group differences for physiological and biomarker secondary outcomes over days 0, 1, 2, 3, 4, and 7. We will not include an interim analysis in this small RCT with only 20 subjects.

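### The SAP's only between-arm analysis of SAEs is a chi-square test; with about 10 patients per arm it should be a risk difference with a named confidence interval

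*SAP*

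**What the plan says.** Protocol section 1.1 (Study Synopsis) puts safety in the primary outcome: "The primary outcome measures will be effectiveness of cooling in achieving and maintaining the target temperature and safety measures". Aim 1 in section 1.2 expects target temperature to be reached and held "without significant increase in serious adverse effects compared with the control arm". The same section states the use of the result: "The proposed pilot study will determine whether we can safely include patients with COVID-19 and ARDS in our larger Phase IIb trial".

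The SAP's descriptive primary analysis names only the two temperature measures, time to target and percent of treatment time in range. For SAEs the whole analysis is "Differences in SAEs will be analyzed by Chi square". It names no risk difference or ratio, interval, unit of count (patients or events), continuity correction or exact alternative. Two-tailed alpha of 0.05 is stated for the ventilator-free-days test and nowhere else. Survival and organ-failure scores are secondary outcomes and fall under other provisions, such as "For secondary clinical outcomes t-tests, Wilcoxon, or chi-square tests will be used as appropriate".

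The protocol also provides for case review of SAEs with a judgement of relatedness, 48-hour reporting, and monthly tables to the safety monitor (sections 2.2.1.1.1, 2.2.3.2 and 12).

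**The concern.** A chi-square test answers whether a difference as large as the observed one would be surprising if the arms were alike. The pilot needs to know how large an excess of SAEs the data still allow. With 20 patients randomized 1:1 those questions come apart: a non-significant result is compatible with no difference and with a very large one, and the p-value does not show which. Because Aim 1 is worded in terms of a significant increase, a non-significant test could easily be taken as reassurance when deciding whether COVID-19 patients enter the Phase IIb trial.

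**Working it through.** **Inputs.** Total 20 subjects (SAP; protocol section 1.1); 1:1 allocation within proning strata (protocol section 3.3), so about 10 v 10. Assumed, because the SAP does not say: patients with at least one SAE as the unit, uncorrected Pearson chi-square, two-sided 0.05. The documents give no SAE rate, margin or target precision, so there is no planned figure to reproduce. The splits below need no assumed rate.

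**Test.** With a patients affected under hypothermia, b under control, and s = a + b, the Pearson statistic at 10 v 10 reduces to

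X² = 20(a - b)² / [s(20 - s)], significant above 3.84.

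- *30-point excess* (a - b = 3): X² = 180 / [s(20 - s)]. It is largest at 3 v 0 and 10 v 7, where 180/51 = 3.53 (p=0.060). All eight possible tables are therefore non-significant (p=0.060 to 0.178).
- *40-point excess* (a - b = 4): X² = 320 / [s(20 - s)]. At 4 v 0 and 10 v 6, 320/64 = 5.00 (p=0.025). At 5 v 1 and 9 v 5, 320/84 = 3.81 (p=0.051). At 6 v 2 and 8 v 4, 320/96 = 3.33 (p=0.068). At 7 v 3, 320/100 = 3.20 (p=0.074). Five of the seven tables are non-significant.
- *50-point excess*: the largest p is 0.025, so all are significant.

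**Interval for 6 v 2.** Wilson 95% limits are 0.313 to 0.832 for 6/10 and 0.057 to 0.510 for 2/10. Newcombe's limits for the risk difference of 0.40 are:

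- lower: 0.40 - √[(0.600 - 0.313)² + (0.510 - 0.200)²] = -0.02
- upper: 0.40 + √[(0.832 - 0.600)² + (0.200 - 0.057)²] = +0.67

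**Largest non-significant split at each control count from 0 to 7:**

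| TH v control | p, two-sided | Newcombe 95%, points |
|---|---|---|
| 3 v 0 | 0.060 | -4 to +60 |
| 5 v 1 | 0.051 | 0 to +68 |
| 6 v 2 | 0.068 | -2 to +67 |
| 7 v 3 | 0.074 | -3 to +67 |
| 8 v 4 | 0.068 | -2 to +67 |
| 9 v 5 | 0.051 | 0 to +68 |
| 9 v 6 | 0.121 | -8 to +60 |
| 10 v 7 | 0.060 | -4 to +60 |

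**Sensitivity to unstated choices.**

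- One-sided at 0.05, 6 v 2 gives 0.068/2 = 0.034, which is significant. So are seven of the eight splits in the table; only 9 v 6 (0.061) is not.
- With Yates' correction or Fisher's exact test, every 40-point table is non-significant (4 v 0: 0.094 and 0.087), and so are some 50-point tables, such as 7 v 2 (0.072 and 0.070).
- The interval method also matters. For 6 v 2, Agresti-Caffo gives -3.8 to +70.5, and the simple Wald interval, +0.8 to +79.2, just excludes zero.
- At 6 v 2 the expected SAE count is 8/2 = 4 per arm, below the usual 5 for relying on the chi-square approximation.

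**The case against.** The strongest reply is that the size of the problem depends on choices the documents do not make. Aim 1 speaks of an increase, so a one-sided test is a fair reading, and then the 6 v 2 example is significant. This stands, and it is why the example must be given with its assumptions. It also supports the point: the same counts give opposite messages according to an unspecified convention.

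A reader might infer that any excess of 30 to 40 points would pass. That is too strong: 4 v 0 and 10 v 6 are significant even under the two-sided assumption, and the table lists the worst case at each control count.

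A reader might also infer that non-significance is the rule for admitting COVID-19 patients to Phase IIb. The documents do not support that. Aim 1 states what the investigators expect, no passage sets a go/no-go criterion, and the protocol elsewhere uses the word significant in a clinical sense, for bleeding for example.

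Nor is safety judged on this p-value alone. In a trial of 20, case review with relatedness assessment may carry more information than any between-arm statistic. That is a fair limit on the weight of the point, but review and tabulation do not estimate the difference between arms.

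Finally, if patient-level counts are published, a reader can compute the interval. True, but the SAP does not commit to those counts or to the unit, and a small pilot is where estimation is preferable to testing.

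**Conclusion.** The concern holds in a limited form. For a component of the primary outcome, the SAP plans a test and no estimate. At 10 v 10, with an uncorrected two-sided 0.05 test, all eight 30-point excesses and five of seven 40-point excesses are non-significant, and in the largest such splits the Newcombe interval reaches about +60 to +68 points. These figures rest on equal arms (not guaranteed under stratification) and on an alpha and test form that the SAP does not state for SAEs. The case for reporting an interval does not rest on those choices. This is a worthwhile, inexpensive improvement; it does not show that the pilot's safety judgement will be wrong.

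**What to change.** Replace the SAP sentence with: *The number and percent of patients with at least one SAE will be reported by arm, with the risk difference (TH minus control) and its 95% Newcombe confidence interval as the main summary. Any p-value is supplementary, and non-significance will not be read as evidence of safety.* Reword the safety part of Aim 1 as estimating the difference in SAE risk between arms.

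As a separate point, the study team should settle one SAE definition and window for this count. Section 2.2.1.1.1 says "Serious Adverse Events are defined as any deaths, life-threatening events, or events that prolong hospitalization that occur within the first three study days"; section 2.2.3.2 refers to "unexpected SAEs occurring in the first study week"; section 12, item 3 ("An AE will be classified as serious if it is fatal or immediately life-threatening") sets no window; and section 12, item 1 keeps ARDS-related death and organ failure out of AE reporting unless study-related. These need to be reconciled.

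The cost is wording and one agreed definition, with no new patients, data or procedures. The drawback is a wide interval. Even at 0 v 0 the Wilson upper limit per arm is 3.84/(10 + 3.84) = 0.28, so the Newcombe interval is about ±28 points and the safety conclusion becomes more cautious. Power is unchanged, since the sample size limits it.

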### 3.3/ Randomization

Subjects will be stratified by proning status at enrollment and randomized within each stratum to receive TH or usual temperature management using a 1:1 assignment ratio. Treatment group assignment will be made using an Excel-based assignment tool stored on the UMB Microsoft OneDrive, which records date, time, and investigator who makes the treatment assignment. Baseline APACHE II, Sequential Organ Failure (SOFA) score 3, driving pressure, P/F ratio, and oxygen saturation index will be documented at time of randomization to assess comparability of disease acuity between groups.

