3.3.2 Randomization Procedures

Randomization will be performed by a macro-driven Excel spreadsheet (CHILL\_COVID\_Assignment\_Tool 1.0) stored on the UMB Microsoft OneDrive:

1. Select “CHILL\_COVID\_Assignment\_Tool 1.0,” click on the 3 vertical dots next to the file title, select “Open” and then on “Open in app.” If opening on a Mac, you will be given the option to enable macros. On a PC, you will have to manually enable macros once the file is open using the following steps:
  - a. Once the file is open, click on the “File” tab
  - b. Click on the “Enable Content” icon (upper left)
  - c. Click on “Advanced Options”
  - d. Select “Enable Content for this Session.”
  - e. The programs should the work.
2. On Sheet 1, Push “Push to Start” button
3. Enter your name from pulldown menu and push “Push to Start” button

4. Enter 3-digit study ID number from pulldown menu and push “Push to Start” button.
5. Re-enter 3-digit study ID number from pulldown menu and push “Push to Start” button.
6. If numbers do not match you will get an error message.
7. Otherwise enter 3-letter identifier and push “Push to Start” button.
8. Enter proning status from pulldown menu and push the “Confirm proning status, then push this button to get assignment” button.
9. The treatment assignment will be displayed in cell B12, all information will be entered along with date/time stamp on Sheet 2.
10. All data are automatically saved and the sheet locked so you just have to click on the close button.

If you make a mistake, make sure you the correct treatment assignment right away and let me know about the entry error so I can fix it. If you put in the wrong proning status, repeat with correct status and let me know so I can fix the error. If you entered wrong patient number or 3-letter code, use the treatment assignment provided and let me know so I can fix the error.

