### 7.2/ Ventilatory and respiratory parameters

Ventilatory and respiratory parameters ( Peak Airway Pressure (Ppeak), Airway Plateau Pressure (Pplat), Positive End Expiratory Pressure (PEEP) and Mean Airway Pressure ( $P_{\overline{aw}}$ ) will be obtained from standard of care mechanical ventilation record. Driving Pressure is calculated as the difference between airway plateau pressure and end-expiratory pressure (Pplat – PEEP) during a breath without spontaneous ventilator effort and Oxygen saturation index (OSI). This will be calculated as the product of mean airway pressure, fraction of inspired oxygen, and 100, divided by pulse oxygen saturation ( $P_{\overline{aw}} \times FIO_2 \times 100/SpO_2$ ) will be calculated and recorded per study data collection requirements.

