**Respiratory Parameters:**

 For the 24 hours preceding randomization, record the lowest measured post-intubation SpO2 date and time of measurement, and the Mean Airway Pressure, measured PEEP, and FiO2 from the nearest time relative to the lowest SpO2 measurement. Record the post-intubation ABG with the lowest PaO2, the date and time that the ABG sample was collected and the Mean Airway Pressure, and FiO2 measured PEEP from the nearest time relative to that ABG. If no ABGs were done, check the None box.

**SpO2:** Lowest SpO2:    %  
 Date/Time of SpO2 measurement:    /   /        
MONTH D D Y Y Y Y TIME (0-2400)

Corresponding Mean Airway Pressure:   cm H2O  
 Corresponding Measured PEEP:   cm H2O  
 Corresponding FiO2:    %

**ABG:** Lowest PaO2:    mm Hg  
 pH:  .   pCO2:    mm Hg  
 Date/Time of ABG collection:    /   /        
MONTH D D Y Y Y Y TIME (0-2400)

Corresponding Mean Airway Pressure:   cm H2O  
 Corresponding Measured PEEP:   cm H2O  
 Corresponding FiO2:   %

None

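### The VFD permutation test states no permutation scheme although randomisation is stratified by proning, and the only adjusted analysis waits for a chance baseline difference; settling both in advance is cheap

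*SAP*

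**What the plan says.** The SAP is one paragraph. On ventilator-free days (VFDs) it states: "The group difference on 28-day VFDs will be tested with a permutation test for the difference in group means with alpha = .05", two-tailed, chosen because many zeros are expected. It names the statistic but not how labels are permuted, and it mentions no strata. On adjustment it states: "If the difference on a baseline prognostic variable is statistically significant, we will perform a secondary analysis to adjust for this variable", by regression. It names no variable and gives no model. The protocol has no statistical section that fills these gaps.

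Protocol section 3.3 describes the design: "Subjects will be stratified by proning status at enrollment and randomized within each stratum", with a 1:1 ratio. No block size is given. In section 3.3.2 the tool issues each assignment after proning status is entered. Section 3.3 also lists severity measures: "Baseline APACHE II, Sequential Organ Failure (SOFA) score 3, driving pressure, P/F ratio, and oxygen saturation index will be documented at time of randomization".

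The Study Synopsis (1.1) makes VFDs a secondary outcome. The Aims (1.2) mark them as primary only within the second aim.

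**The concern.** A permutation test is defined by its set of permutations. Free shuffling and shuffling within strata can give different p-values on the same 20 patients. The trial is unblinded, so the choice should be fixed before outcomes are seen. When randomisation is stratified, the natural analysis permutes within the strata. Free shuffling counts between-stratum variation as noise that a blocked design has already removed.

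The significance trigger is a separate matter. In a properly randomised trial a significant baseline difference is a chance event and says nothing about how strongly the variable predicts VFDs. Whether an adjusted analysis exists, and on which variable, is therefore left to luck.

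Power and analyst discretion are at stake, on the only outcome for which the SAP states an alpha. The safety and feasibility decision does not rest on this p-value.

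**Working it through.** **No planned figure to reproduce.** The SAP states 20 subjects and alpha .05, but no power, effect size or SD.

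**1. The trigger.** For k independent baseline variables tested at 5%, the chance of at least one significant result is 1 − 0.95^k.
- k = 1: 5%.
- k = 4: 1 − 0.8145 = 18.5%.
- k = 5: 1 − 0.7738 = 22.6%.

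Five is the number of measures listed in section 3.3. Four applies if APACHE II is left out, since the Baseline Data form shows no field for its score or for a coma score. The SAP does not limit the trigger to that list, so k is an assumption. Correlation lowers the figure: for five variables with pairwise correlation 0.7 it is about 15%.

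**2. Free versus stratified permutation.** All effects here are assumed. VFD is 0 with probability p, otherwise Normal(m, SD 5), rounded and limited to 1–28. Mean VFD is about (1 − p) × m in each stratum:
- (a) proning not prognostic: 0.55 × 14 = 7.7 in both.
- (b) moderate: 0.625 × 16 = 10.0 against 0.475 × 12 = 5.7.
- (c) strong: 0.70 × 18 = 12.6 against 0.40 × 10 = 4.0.

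Treatment lowers p by 0.25 and raises m by 4. The stratified statistic weights each stratum difference by n1·n0/(n1+n0). Simulation error is about 0.45 points for power and 0.25 for size. Power, free → stratified:

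| Strata, allocation | (a) | (b) | (c) |
|---|---|---|---|
| 10/10, blocks of 2 | .386 → .383 | .363 → .400 | .284 → .447 |
| 10/10, blocks of 4 | .380 → .378 | .359 → .392 | .286 → .442 |
| 10/10, simple | .375 → .360 | .361 → .373 | .317 → .411 |
| 6/14, blocks of 2 | .388 → .386 | .341 → .373 | .256 → .384 |
| 6/14, blocks of 4 | .391 → .385 | .348 → .377 | .262 → .379 |
| 6/14, simple | .381 → .363 | .337 → .340 | .289 → .356 |

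By subtraction, in percentage points:
- Blocked allocation: −0.2 to −0.6 in (a), +2.9 to +3.7 in (b), +11.7 to +16.3 in (c).
- Simple allocation: −1.5 to −1.8, +0.3 to +1.2 and +6.7 to +9.4.

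Size of the free test when blocked was 4.4–4.9% in (a), 3.9–4.5% in (b) and 2.2–2.7% in (c). The stratified test held 4.2–5.1% throughout.

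**3. Check with a different outcome model.** This used a censored normal outcome, blocks of 4, half the patients prone and stratum effects of 0, 0.5, 1 and 1.5 SD. Simulation error was about 1.1 points for power. Free versus stratified power was 48.4/48.2, 47.2/49.2, 39.3/47.2 and 26.2/40.4%. Size of the free test was 5.2, 3.8, 3.4 and 1.9%. The pattern is the same.

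**4. Adding one covariate to the stratified analysis** (first model). Power changed by −1.7 to +0.1 points if the covariate was unrelated to VFDs, by +0.9 to +3.0 at latent correlation 0.3, and by +5.9 to +8.4 at 0.5.

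**5. Cost when nothing is prognostic and allocation is simple.** Both changes together, first model: .384 → .356 (−2.8) and .380 → .360 (−2.0). Second model, half prone: stratifying alone .475 → .446 (−2.9); with an unrelated covariate as well, .431 (−4.4).

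**6. Feasibility.** Two strata of 10 split 5/5 give 252 × 252 = 63,504 arrangements, against 184,756 unrestricted, so a two-sided 5% result is attainable. Section 2.2.1.2.1 already lists stratum and assignment for each patient. For oxygen saturation index (OSI), section 7.2 gives the formula: "This will be calculated as the product of mean airway pressure, fraction of inspired oxygen, and 100, divided by pulse oxygen saturation". Line 15 of the Baseline Data form records the lowest SpO2 with its FiO2 and "Corresponding Mean Airway Pressure".

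**The case against.** The strongest reply is that little is at stake. VFDs are secondary, the SAP seeks only trends, and simulated power is below 50% under either scheme without a covariate. In scenario (a) stratifying loses a little power in every cell. Double-digit gains need a gap between strata that no document supports. All of this stands, and it is why the change is cheap but not free. The fix also alters the named statistic, although with exact 1:1 balance in each stratum the weighted and simple mean differences coincide.

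If the schedule is blocked, strict design-matching would permute within blocks. In the first model that loses a further 4 to 7 points with blocks of 2 and 1 to 3 with blocks of 4. Within-stratum permutation under blocking and an assumed enrolment drift had size 2.9–4.0%: conservative, not inflated.

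Three stronger readings are tempting and unsupported:
- **That the planned test is invalid.** Free shuffling was at or below nominal size, within simulation error, in both models.
- **That P/F ratio cannot serve as the covariate.** A reader might infer this from the Baseline Data form's "If no ABGs were done, check the None box". But section 3.3.1 allows P/F to be imputed from SpO2, a qualifying value is required for randomisation, and section 10.1 and the P/F Ratio Table (line 13 of the randomisation form) record it as measured or inferred.
- **That a mistaken proning entry uses up a place in the other stratum's schedule.** Section 3.3.2 says only: "If you put in the wrong proning status, repeat with correct status and let me know so I can fix the error". Whether the place is lost or restored is not stated.

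**Conclusion.** The concern holds as a cheap improvement of low consequence. The SAP leaves the permutation scheme open despite stratified randomisation and makes covariate adjustment depend on chance. Neither is a validity error.

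The power gain is conditional. With blocked allocation it is about 3 points if proning is moderately prognostic, 12 to 16 if strongly so, and none if it is not prognostic; with simple allocation it is smaller. These sizes rest on assumed VFD distributions, stratum splits, block sizes and treatment effect, so no single gain can be claimed. The covariate gain applies only to the secondary adjusted analysis, not to the alpha .05 test.

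The downside is about 3 power points if neither proning nor the covariate is prognostic and allocation is unblocked. The least favourable cell of the second model put the two changes together nearer 4, with simulation error of about 1 point.

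**What to change.** State in the SAP:

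> The VFD permutation test will permute treatment labels within the proning stratum under which the assignment used was drawn, with the realised arm sizes per stratum held fixed. The statistic is the stratum-adjusted difference in mean VFDs (weights n1·n0/(n1+n0)).

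Replace the significance trigger with:

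> One secondary adjusted analysis will regress VFDs on treatment, proning stratum and baseline OSI (formula in Protocol section 7.2, using the lowest-SpO2 set on line 15 of the Baseline Data form), with labels permuted within strata, and will be reported whatever the baseline comparisons show.

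The line must be named because line 22 of the same form holds a second, most-recent set of SpO2 and mean airway pressure. The P/F ratio on the randomisation form is an acceptable alternative to OSI, but only one covariate should be chosen in advance.

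Reconcile the stratum definition. Section 3.3 fixes proning status at enrolment. Section 10.1, line 15 of the randomisation form and line 14 of the Summary of Patient Outcomes take it at randomisation. Section 5 allows a wait between the two.

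The cost is a few sentences and the small conditional power loss given above. No new data and no extra patients are needed.
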